5.2 Exclusion Criteria

1. Known allergy to any of the study medications, their analogues, or excipients in the various formulations.
2. Treatment with any investigational products within 28 days before the first dose of study drug.
3. Requirement for other concomitant chemotherapy, immunotherapy, radiotherapy, or any ancillary therapy considered to be investigational.
4. Failure to have fully recovered (ie, \leq Grade 1 toxicity) from the effects of prior chemotherapy regardless of the interval since last treatment.
5. Cardiac system:
 - a. QTc $>$ 470 milliseconds (msec) on a 12 lead ECG obtained during the Screening period. If a machine reading is above this value, the ECG should be reviewed by a qualified reader and confirmed on a subsequent ECG.
 - b. AL Amyloidosis Risk Stage III disease. Staging defined by: NT-proBNP cut off of $<$ 332 pg/mL and troponin T cut-off of 0.035 ng/mL as thresholds: stage III, both over threshold; if troponin T not available at local institution, troponin I may be used, but threshold is $<$ 0.1 ng/mL⁽⁵⁷⁾
 - c. New York Heart Association (NYHA) classification III or IV. See Section 15.4 for criteria.
 - d. Enzyme-documented myocardial infarction within 6 months before enrollment.
 - e. Chronic atrial fibrillation.
 - f. Grade 2 or 3 atrioventricular (AV) block (Mobitz, Type I permitted).
 - g. Sustained ($>$ 30 seconds) ventricular tachycardia, more than 1 episode of nonsustained ventricular tachycardia (defined as 3 consecutive ventricular beats), or frequent ($>$ 20/24 hours) ventricular pairs, detected by 24-hour ambulatory electrocardiographic monitoring.
 - h. Supine systolic blood pressure $<$ 90 mmHg, or symptomatic orthostatic hypotension, or a decrease in systolic blood pressure on standing of $>$ 20 mm Hg in spite of being treated for orthostatic hypotension.
 - i. History of a bleeding diathesis or currently receiving treatment with warfarin. Patients are allowed to take aspirin.

7. GI system:

- a. Severe diarrhea (\geq Grade 3) not controllable with medication (such as octreotide) or requires administration of total parenteral nutrition.
- b. Known GI disease or GI procedure that could interfere with the oral absorption or tolerance of study drug, including difficulty swallowing.

8. Neurologic/ Social system:

- a. Patients with \geq Grade 2 peripheral neuropathy or painful peripheral neuropathy on clinical examination will be excluded.
- b. Previous or ongoing psychiatric illness and/or social situations that would limit compliance with study requirements.

9. Systemic infections:

- a. Known to be human immunodeficiency virus (HIV)-positive.
- b. Known to be hepatitis B surface antigen-positive or has known or suspected active hepatitis C infection.
- c. Uncontrolled infection requiring systemic antibiotics.

10. Other malignant disease/s:

- a. Clinically overt multiple myeloma (bone marrow plasma cells \geq 30%), and at least 1 of the following: bone lesions, anemia (< 100 g/L), and hypercalcemia.
- b. Patients with amyloidosis due to mutations of the transthyretin gene (see Section 15.2).
- c. Patients with non-AL amyloidosis (see Section 15.2).
- d. Presence of other active malignancy with the exception of nonmelanoma skin cancer, cervical cancer, treated early-stage prostate cancer provided that prostate-specific antigen is within normal limit, or any completely resected carcinoma in situ.

11. Female patients who are lactating or pregnant.

12. Major surgery within 14 days before the first dose of study drug.

13. Systemic treatment with strong inhibitors of CYP1A2 (fluvoxamine, enoxacin, ciprofloxacin), strong inhibitors of CYP3A (clarithromycin, telithromycin, itraconazole, voriconazole, ketoconazole, nefazodone, posaconazole) or strong CYP3A inducers

(rifampin, rifapentine, rifabutin, carbamazepine, phenytoin, phenobarbital), or use of Ginkgo biloba or St. John's wort within 14 days before the first dose of study treatment.

14. Any other serious medical or psychiatric illness that could, in the investigator's opinion, potentially interfere with the completion of treatment according to this protocol.

6. DESCRIPTION OF TREATMENT

6.1 Study Drug

The study drug will be administered at the Amyloidosis Research and Treatment Center. The treatment schedule for each patient will be provided to the Intensive Care Department at least 1 week before commencing each treatment cycle. The Intensive Care Unit will grant availability on the days of MLN9708 administration, in the event that any adverse events occur that require emergency or intensive care.

All protocol-specific criteria for administration of study drug must be met and documented prior to drug administration. Study drug will be administered only to eligible patients under the supervision of the investigator or identified subinvestigator(s). Patients should be monitored for toxicity as necessary and doses of MLN9708 should be modified as needed to accommodate patient tolerance to treatment; this may include symptomatic treatment, dose interruptions and adjustments of MLN9708 dose. All doses must be taken as outlined in the Schedule of Events. No doses should be missed or delayed during Cycle 1 due to patient scheduling. Following agreement between the investigator and the sponsor, eligible patients may take study drug at home as directed.

Refer to Study Manual for additional instructions regarding study drug administration.

MLN9708 Administration

The study drug should be taken on an empty stomach, at least 1 hour before or no sooner than 2 hours after a meal. The capsules should not be chewed, broken, or opened for administration. Each capsule should be swallowed separately with approximately 240 mL (ie, 8 oz) total of water with the full dose. MLN9708 will be given as a single daily oral dose. The dose will be assigned based on the dose-escalation methodology outlined in [Table 6-1](#). Administration of the capsules may be guided by the dosing tables included in the pharmacy manual.

The prescribed administration of MLN9708 doses in this study is weekly x 3 followed by 1 week without MLN9708 in a 28-day cycle. Missed doses can be taken as soon as the patient remembers as long as the next scheduled dose is 70-72 hours or more away. Patients who vomit after ingestion will not receive an additional dose, but should resume dosing at the time of the next scheduled dose.

Dexamethasone Administration

If a patient does not have a response after 3 cycles of MLN9708 treatment, dexamethasone will be added. Dexamethasone will be given as a single, oral dose of 40 mg/day on Days 1 through 4 of a 28-day cycle beginning with Cycle 4. For patients with fluid retention > 3% of body weight despite optimal diuretic therapy a starting dose of dexamethasone 20 mg should be considered.

Dexamethasone should be taken at approximately the same time each day. Dexamethasone should be taken approximately 1 hour after MLN9708. Each dose of dexamethasone should be taken with food or milk.

If a dose of dexamethasone is missed, the dose should be taken as soon as the patient remembers it. A double dose should not be taken to make up for a missed dose. If the patient vomits after taking a dose, the patient should not repeat the dose but should resume dosing at the time of the next scheduled dose.

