- g 24-hour Holter monitor, to be performed at screening, and at any time the physician believes it is medically appropriate.
- h A full physical exam will occur every 3 cycles. Symptom-directed assessments will be conducted per standard clinical practice.
- i Should occur every 3 cycles.
- j A serum pregnancy test will be performed for women of childbearing potential during screening and predose on Cycle 1, Day 1. The serum pregnancy test may be collected up to 3 days before dosing. The results must be available and negative before the first dose of MLN9708 is administered.
- k Hematology and chemistry panels may be collected up to 3 days prior to dosing. Criteria for retreatment are provided in Section 6.5.2. After 24 cycles on treatment, hematology and chemistry laboratory evaluations may be done to monitor the patient according to standard clinical practice per the treating physician.
- l Repeat as clinically indicated by change in serum creatinine. Creatinine clearance will be calculated based on a 24-hour urine collection at screening. eGFR will be calculated according to the equations in Section 15.1. 24-hour urine for protein is required to assess amyloid renal involvement/ response.
- m If abnormal, a diagnostic work up should be performed and the patient treated and stabilized before administering MLN9708. PT/INR and PTT may be repeated during the treatment period at the discretion of the investigator if bleeding occurs or as clinically indicated.
- n Only for patients in the extension cohort after every cycle.
- o Repeat every treatment cycle, at the EOT visit, and every 6 weeks during the PFS follow-up period.
- p CCI
- q Bone marrow biopsy and aspirate should be repeated at the discretion of the investigator as clinically indicated and if response is documented by other parameters, and at EOT. Immunohistochemistry of dominant clonal plasma cells is recommended.
- r To be performed at screening and at any time the physician believes there are symptoms or signs that suggest increased or new bone lesions. Plain films of symptomatic sites for signs or symptoms of new bone lesions may be obtained instead of a full skeletal survey. A PET-CT may be done at screening in

Study Procedures	Screening ^a	Treatment Period					End of Treatment ^d	Follow-up	
		CYCLES 1 -12 ^b						PFS ^e (± 1 wk)	OS ^f (± 1 wk)
	Days	Days				Every 6 weeks		Every 6 weeks	Every 12 weeks
	-28 to -1	1 ^c	8	15	Rest Period 22 to 28	Every 6 weeks		Every 12 weeks	Every 12 weeks

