1.3 Clinical Experience

MLN9708 is a boronic acid proteasome inhibitor similar to VELCADE. Clinical studies with VELCADE have yielded a detailed understanding of its safety profile. For details, refer to the package insert for VELCADE.⁽⁵⁰⁾ MLN9708 is in the early stages of clinical

investigations in humans with safety, tolerability, PK, pharmacodynamics, electrocardiogram (ECG) parameters, and disease response assessed in each study.

MLN9708 is the first investigational proteasome inhibitor with substantial oral bioavailability in patients with MM.

As of 24 September 2010, 112 patients have been treated with single-agent MLN9708 across 4 phase 1 studies (C16001, IV administration twice weekly in adult patients with advanced nonhematologic malignancies, n = 67; C16002, IV administration weekly in adult patients with advanced lymphoma, n = 11; C16003 and C16004 PO administration twice weekly and weekly, respectively, in adult patients with relapse or refractory multiple myeloma, n = 19 and 15, respectively). Regardless of the route of administration in the twice-weekly dosing schedule, MLN9708 is given on Days 1, 4, 8, and 11 of a 21-day cycle and, in the weekly dosing schedule, the drug is given on Days 1, 8, and 15 of a 28-day cycle.

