6.15 Storage, Handling, and Accountability

Upon receipt at the investigative site, MLN9708 should remain in the blister and carton provided until use or until drug is dispensed. The container should be stored at the investigative site refrigerated (36°F to 46°F, 2°C to 8°C). All excursions should be brought to the sponsor's attention for assessment and authorization for continued use. Ensure that the drug is used before the retest expiry date provided by Millennium. Expiry extensions will be communicated accordingly with updated documentation to support the extended shelf life.

In countries where local regulations permit, MLN9708 capsules dispensed to the patient for take-home dosing should remain in the blister packaging and refrigerated as noted above

until the point of use. The investigative site is responsible for providing the medication to the patient in the correct daily dose configurations. Approval for any patient for take-home medication must be discussed with Millennium in order to ensure the greatest conformity with repackaging, labeling, and patient compliance. Comprehensive instructions should be provided to the patient in order to ensure compliance with dosing procedures. Patients who are receiving take-home medication should be given only 1 cycle of medication at a time. Patients should be instructed to store the medication refrigerated (36°F-46°F, 2°C-8°C) for the duration of each cycle. Patients should be instructed to return their empty blister packs to the investigative site, rather than discarding them. Reconciliation will occur accordingly when the patient returns for their next cycle of take-home medication. Any extreme in temperature should be reported as an excursion and should be dealt with on a case-by-case basis.

Because MLN9708 is an investigational agent, it should be handled with due care. Patients should be instructed not to chew, break, or open capsules. In case of contact with broken capsules, raising dust should be avoided during the clean-up operation. The product may be harmful by inhalation, ingestion, or skin absorption. Gloves and protective clothing should be worn during cleanup and return of broken capsules and powder to minimize skin contact. The area should be ventilated and the site washed with soap and water after material pick-up is complete. The material should be disposed of as hazardous medical waste in compliance with federal, state, and local regulations.

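### Section 6.1 lets a missed Day 15 dose be made up inside the rest week that it prescribes, as late as about Day 26, leaving 3 to 7 days before the next cycle instead of 14

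*Protocol*

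**What the plan says.** Protocol Section 6.1 (MLN9708 Administration) gives the schedule as "weekly x 3 followed by 1 week without MLN9708 in a 28-day cycle". Doses fall on Days 1, 8 and 15 (Section 4.1), and the Schedule of Events labels Days 22 to 28 as the rest period. The next sentence of 6.1 is the missed-dose rule: "Missed doses can be taken as soon as the patient remembers as long as the next scheduled dose is 70-72 hours or more away". It makes no exception for Day 15, does not mention the rest week and is not limited to particular cycles.

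Other text bears on how the rule would work:

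- Section 6.1 also says "All doses must be taken as outlined in the Schedule of Events", and it bars missing or delaying Cycle 1 doses for reasons of patient scheduling.
- With sponsor agreement, "eligible patients may take study drug at home as directed" (6.1).
- Section 6.15 adds: "Patients who are receiving take-home medication should be given only 1 cycle of medication at a time". It continues: "Reconciliation will occur accordingly when the patient returns for their next cycle of take-home medication".
- Schedule of Events, footnote k: "Hematology and chemistry panels may be collected up to 3 days prior to dosing". Section 7.5.10 states the same allowance as 72 hours.

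The SAP contains no missed-dose rule.

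**The concern.** Two adjacent sentences give different answers for the same patient. On Days 16 to 21 a make-up of the Day 15 dose satisfies both. From Day 22 to about Day 26 it satisfies the missed-dose rule and breaks the week off. The rule works for Days 1 and 8, where the next dose is a week away. It behaves differently for Day 15 because it counts across the rest week to the next cycle.

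What is at stake is the recovery interval before three more weekly doses. Retreatment requires neutrophils of at least 1 and platelets of at least 75 x 10^9/L (6.5.2.1), and a check made before a late make-up dose says nothing about that dose. Home dosing is where this could happen unnoticed: the patient can hold the Day 15 capsules at home, the rule turns on when the patient remembers, and capsules are reconciled only at the return for the next cycle.

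**Working it through.** No sample-size or error-rate formula applies; this is calendar arithmetic.

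**Inputs.** Doses on Days 1, 8 and 15 of a 28-day cycle, so the next dose after Day 15 is Day 29. Rest period Days 22 to 28. Minimum gap to the next scheduled dose 70 to 72 hours. Assumptions: same clock time each day, and the next cycle starts on time.

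**Latest make-up day** = next scheduled day - 3 (72 hours; with 70 hours, 2 hours later the same day).

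| Missed dose | Next dose | Latest make-up | Window |
|---|---|---|---|
| Day 1 | Day 8 | 8 - 3 = Day 5 | 4 days |
| Day 8 | Day 15 | 15 - 3 = Day 12 | 4 days |
| Day 15 | Day 29 | 29 - 3 = Day 26 | 11 days |

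Days 27 and 28 (48 and 24 hours before Day 29) are excluded. In a patient's final cycle there is no next scheduled dose, so the rule sets no limit.

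**Interval to the next cycle** = 29 - d, and full drug-free days = 28 - d, for a last dose on Day d.

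| Last dose | Days to Day 29 | Full drug-free days |
|---|---|---|
| Day 15 (planned) | 14 | 13 |
| Day 21 | 8 | 7 |
| Day 22 | 7 | 6 |
| Day 23 | 6 | 5 |
| Day 24 | 5 | 4 |
| Day 25 | 4 | 3 |
| Day 26 | 3 | 2 |

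**Comparison.** In the sponsor's twice-weekly studies, "MLN9708 is given on Days 1, 4, 8, and 11 of a 21-day cycle". That schedule also has 3-day gaps, but the last dose is followed by 22 - 11 = 11 days before the next cycle.

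**Total drug through Day 43.** Planned: Days 1, 8, 15, 29, 36, 43 = 6 doses. With a Day 26 make-up: Days 1, 8, 26, 29, 36, 43 = 6 doses. The make-up follows a gap of 26 - 8 = 18 days. Total drug is unchanged, but the last four doses are closer together: 43 - 26 = 17 days from first to last, against 43 - 15 = 28 as planned and 43 - 21 = 22 for a Day 21 make-up.

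**Counts.** The pre-cycle panel may be drawn from 29 - 3 = Day 26. A make-up on Days 22 to 25 therefore precedes any permitted pre-cycle panel. Only a make-up on Day 26 itself can come after the panel. If the limit is kept in hours (72 in Section 7.5.10), the overlap is at most the 2 hours between 72 and 70. In that case, if the rest-period panel was also drawn before the make-up, the next scheduled panel is Day 8 of the next cycle: Day 28 + 8 = 36, or Day 33 at the earliest. That is 33 - 26 = 7 to 36 - 26 = 10 days after the make-up dose, and after the Day 29 dose.

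**The case against.** The best defence is that the missed-dose sentence is permissive, while the schedule and the duty to follow it are mandatory. Read together, they let a late dose be taken within the dosing weeks and keep the week off. That is probably what was intended. It does not settle the text, because every make-up dose departs from the Schedule of Events; if that duty controlled, the missed-dose rule would have no effect at all.

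Several safeguards do stand, in part:

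- Patients are checked for toxicity every week (6.5.1). Haematology is scheduled on Day 15 and in the rest period, and response assessment falls on Days 22 to 28 (7.5.12.1). A missed dose has several chances to surface.
- Table 6-2 withholds drug at platelets of 30 x 10^9/L or less, or neutrophils of 0.75 x 10^9/L or less, on a dosing day other than Day 1. By its wording this covers a make-up day, but nothing schedules a count on the day a patient at home remembers.
- Section 6.5.2 can delay the next cycle if counts have not recovered, but it does not stop the rest-week dose.
- Section 6.1 refers to the Study Manual, and 6.15 requires full dosing instructions for patients at home. Either may contain a limit.

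A reader might infer three stronger points that the documents do not support. The first is overdosing: the number of doses is unchanged and a Day 26 make-up follows an 18-day gap. The second is that 3-day spacing is itself the fault: the rule also allows it between Days 5 and 8 and between Days 12 and 15, and the twice-weekly studies used it. The third is that the MTD decision is compromised by Cycle 1 patients with too little observation after a late dose. Every patient has Day 15 sampling from predose through 24 hours and again on Day 22, so an unnoticed Day 15 miss in Cycle 1 is implausible. Events meeting DLT criteria in later cycles are also weighed for the RP2D (6.4).

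**Conclusion.** The contradiction in 6.1 is real. Followed literally, the missed-dose rule allows a Day 15 make-up on Days 22 to about 26, cutting the interval before the next cycle from 14 days to between 3 and 7. It is a low-frequency safety inconsistency, relevant mainly to home dosing in Cycle 2 and later. The gap in the count check is narrower still, since it needs a make-up on Day 26 after the panel was drawn.

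The documents give no rate of missed doses, so expected occurrences cannot be estimated. The conclusion assumes that the next cycle starts on Day 29, that the dose was forgotten rather than withheld for toxicity (Section 6.6 governs those), and that no limit in the Study Manual overrides the protocol text. It does not bear on the DLT-evaluable definition, the MTD or the sample size.

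**What to change.** In Section 6.1, replace the 70-to-72-hour range with a single 72-hour cut-off. Add that, in any cycle, a missed Day 15 dose may be taken no later than Day 21 and is otherwise skipped, so that Days 22 to 28 stay free of MLN9708. If the Study Manual already has such a limit, bring it into 6.1.

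The make-up window for Day 15 becomes 21 - 15 = 6 days instead of 11, still longer than the 4 days for Days 1 and 8. A Day 22 limit would also keep a 7-day interval, but Day 22 lies in the labelled rest period, so the two sentences would still conflict.

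The cost is an occasional skipped dose. In Cycle 1 without a DLT, a skipped dose makes the patient not DLT-evaluable. The existing text covers this: Section 6.3.1 requires replacement, while Section 7.9 only permits it. Neither Protocol 8.1.3 nor SAP 2.2 needs to change.

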6.2 Reference/Control Therapy

There is no reference group in this study.

6.3 Definitions of Dose-Limiting Toxicity (DLT)

6.3.1 DLT Definitions

Although DLTs may occur at any point during treatment, only DLTs occurring during Cycle 1 of treatment must influence decisions regarding dose-escalation, expansion of a dose level, or evaluation of intermediate dose levels. However, DLTs occurring in later cycles may be taken into consideration for dose-escalation decisions, at the discretion of the investigators and sponsors.

Toxicity will be evaluated according to the National Cancer Institute Common Terminology Criteria for Adverse Events (NCI CTCAE), version 4.03.⁽⁵⁸⁾ Toxicity will be evaluated

according to the National Cancer Institute Common Terminology Criteria for Adverse Events (NCI CTCAE), version 4.03. ⁽⁵⁸⁾ DLT will be defined as any of the following AEs that are considered by the investigator to be even possibly related to therapy with MLN9708:

- Any Grade 4 thrombocytopenia (platelets < 25, 000/mm³) lasting at least 7 days.
- Grade 3 thrombocytopenia with clinically significant bleeding, where clinically significant bleeding is defined as a blood loss of > 100 cc or the requirement for a RBC transfusion.
- A platelet count < 10,000/mm³.
- Any Grade 4 neutropenia (ANC < 500/mm³) lasting at least 7 days or Grade 3 febrile neutropenia with fever and/or infection where fever is defined as a temperature $\geq 38.5^{\circ}\text{C}$.
- Grade 2 peripheral neuropathy with pain or Grade 3 or greater peripheral toxicity.
- Any Grade 3 or higher nonhematologic toxicity (in particular, worsening neuropathy, diarrhea despite maximal supportive therapy, life-threatening ventricular arrhythmia or atrial arrhythmia with hemodynamic instability, fluid retention that does not resolve with 3 or 4 days of intravenous diuretic therapy and bedrest, symptomatic congestive heart failure, and hypotension); with the following exceptions: Grade 3 arthralgia/ myalgia and brief (< 1 week) Grade 3 fatigue.
- Grade 3 or greater nausea and/or emesis despite the use of optimal anti-emetic prophylaxis. Optimal anti-emetic prophylaxis is defined as an anti-emetic regimen than employs 5-HT₃ antagonist given according to standard practice.
- A delay of more than 2 weeks in the initiation of Cycle 2 of treatment because of a lack of adequate recovery of MLN9708-related hematological or nonhematologic toxicities.

- Other MLN9708-related nonhematologic toxicities Grade 2 or greater that, in the opinion of the investigator, requires discontinuation of therapy with MLN9708.

[figure not shown]
Patients who do not receive all doses of MLN9708 in Cycle 1 for reasons other than DLTs will be replaced within the cohort. Patients who receive all doses of MLN9708, yet for unforeseen circumstances recovery of toxicity is not available and safety in Cycle 1 cannot be fully evaluated may be replaced within the cohort.

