6.5 Dose-Modification Guidelines

6.5.1 Dose-Modification Guidelines

During the study, the focus of the evaluations is on the assessment of toxicity to document the occurrence of DLT. Although DLTs may occur at any point during treatment, only DLTs occurring during Cycle 1 of treatment must influence decisions regarding dose-escalation, expansion of a dose level, or evaluation of intermediate dose levels. However, DLTs occurring in later cycles may be taken into consideration for dose-escalation decisions, at the discretion of the investigators and sponsors. Unless a DLT is documented to have occurred, no dose modification is allowed during Cycle 1. Dose-limiting toxicities (DLTs) are defined in Section 6.3.1. In the event that a patient experiences DLT during Cycle 1, treatment should be held and the event will be counted toward the assessment of MTD for the given cohort. Patients experiencing DLTs in Cycle 1 may be restarted following recovery from toxicity at the discretion of the investigator according to the guidelines provided in Section

6.5.2 and Section **6.6**. If a decision is made to restart MLN9708 therapy following a DLT, the MLN9708 dose must be reduced 1 dose level.

The patient will be evaluated weekly for possible toxicities that may have occurred after the previous dose(s). Toxicities are to be assessed according to the NCI CTCAE, version 4.03.⁽⁵⁸⁾ Prior to beginning the next cycle of treatment, refer to the guidelines in Sections **6.5.2** and **6.6**. Further clarification can be obtained in consultation with the Millennium clinician (or designee). If multiple toxicities are noted, the dose adjustments and/or delays should be made according to the most severe toxicity guidelines.

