6.6.1 MLN9708 Dose Adjustments for Hematologic Toxicity

Dosage adjustments for hematologic toxicity are outlined in [Table 6-2](#).

Table 6-2 MLN9708 Dose Adjustments for Hematologic Toxicities

Criteria	Action
Within-Cycle Dose Modifications	
If platelet count $\leq 30 \times 10^9/L$ or ANC $\leq 0.75 \times 10^9/L$ on a MLN9708 dosing day (other than Day 1)	MLN9708 dose should be withheld. Complete blood count (CBC) with differential should be repeated at least every other day until the ANC and/or platelet counts have exceeded the prespecified values (see Section 6.5.2.1) on at least 2 occasions. In the event CBC cannot be repeated at least every other day, dose modifications should be made in consultation with sponsor. Upon recovery, MLN9708 may be reinitiated with 1 dose level reduction or by 33% if the patient is receiving the first dose level.
Dose Modifications for Subsequent Treatment Cycles	
Delay of > 2 weeks in the start of a subsequent cycle due to lack of toxicity recovery as defined in Section 6.5.2 :	
 - Hold MLN9708 until resolution as per criteria Section 6.5.2. - Reduce MLN9708 1 dose level or 33% if the patient is receiving the first dose level. - The maximum delay before treatment should be discontinued (except in the case of investigator determined clinical benefit and discussion with the Millennium clinician) will be 3 weeks.
Dose Modifications for Subsequent Treatment Cycles	
All hematologic toxicities	For hematologic toxicity that occurs during a cycle but recover in time for the start of the next cycle, a dose level reduction will be made either based on within-cycle or for

Table 6-2 MLN9708 Dose Adjustments for Hematologic Toxicities

Criteria	Action
	subsequent cycle criteria, but not for both from the same cycle.

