8.1.3 Populations for Analysis

The populations used for analysis will include the following:

Safety Population: Patients who receive at least 1 dose of MLN9708. The safety population will be used for safety analyses.

DLT-evaluable Population: Patients who receive all Cycle 1 doses of MLN9708 or experience a DLT in Cycle 1. The DLT-evaluable population will be used to determine the MTD.

Organ Response-Evaluable Population: The organ response-evaluable population is defined

as patients who receive at least 1 cycle of MLN9708, have amyloid involvement of at least kidney or heart at baseline, and at least 1 post-baseline organ response assessment.

Hematologic Response-Evaluable Population: The hematologic response-evaluable population is defined as patients who receive at least 1 cycle of MLN9708, have measurable disease at baseline, and at least 1 post-baseline hematologic response assessment.

Plasma PK Analysis Population: Patients who:

- a. Receive full doses of MLN9708 during Cycle 1 without dose reduction or interruptions through the completion of PK sampling
- b. Do not receive any excluded concomitant medications
- c. Have sufficient plasma MLN2238 concentration-time data to permit reliable estimation of plasma PK parameters

Pharmacodynamic Analysis Population: Patients who:

- a. Receive full doses of MLN9708 during Cycle 1 without dose reduction or interruptions
- b. Do not receive any excluded concomitant medications through the completion of pharmacodynamic sampling
- c. Have sufficient whole blood 20S proteasome inhibition-time data to permit reliable estimation of pharmacodynamic parameters

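### The bleeding DLT criterion names Grade 3 thrombocytopenia only, so a short Grade 4 episode with the same bleed meets no platelet DLT criterion

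*Protocol*

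**What the plan says.** Protocol 6.3.1 (DLT Definitions) has three platelet criteria:

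1. Grade 4 thrombocytopenia, given as below 25,000/mm³, lasting at least 7 days.
2. "Grade 3 thrombocytopenia with clinically significant bleeding, where clinically significant bleeding is defined as a blood loss of > 100 cc", or a requirement for red cell transfusion.
3. Any platelet count below 10,000/mm³.

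The neutropenia criterion has the same form: Grade 4 "lasting at least 7 days or Grade 3 febrile neutropenia with fever and/or infection where fever is defined as a temperature" of at least 38.5°C. Other items in the list are open-ended upward. The general one reads "Any Grade 3 or higher nonhematologic toxicity", and the neuropathy and nausea/emesis items also extend above Grade 3. Two further criteria could apply to a bleeding patient: a delay of more than 2 weeks in starting Cycle 2, and "Other MLN9708-related nonhematologic toxicities Grade 2 or greater that, in the opinion of the investigator, requires discontinuation of therapy with MLN9708".

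Three other provisions decide what happens to a patient whose event is not a DLT:

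- Protocol 6.5.1: "Unless a DLT is documented to have occurred, no dose modification is allowed during Cycle 1".
- Protocol Table 6-2, for platelets at or below 30 × 10⁹/L on a dosing day other than Day 1: "MLN9708 dose should be withheld. Complete blood count (CBC) with differential should be repeated at least every other day". The table does not limit this to later cycles.
- Protocol 6.3.1: "Patients who do not receive all doses of MLN9708 in Cycle 1 for reasons other than DLTs will be replaced within the cohort". Section 8.1.3 defines the DLT-evaluable population as "Patients who receive all Cycle 1 doses of MLN9708 or experience a DLT in Cycle 1". SAP 2.2 has the same definition, restricted to dose escalation.

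**The concern.** The criterion runs the wrong way across its boundary. A significant bleed at 30,000/mm³ is a DLT. The same bleed at 15,000/mm³, with counts recovering inside a week, meets no platelet criterion. Because neighbouring items spell out *or higher* or *or greater*, a literal reader has grounds to treat the bare grade as exact. Nothing elsewhere in the protocol or SAP extends it.

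Cycle 1 DLTs drive escalation under Protocol 6.4, and the MTD/RP2D is a primary endpoint (3.1). With 3 to 6 evaluable patients per level, one misclassified patient can change a decision: 1 of 3 becomes 0 of 3 and the added cohort is skipped, or 2 of 6 becomes 1 of 6 and escalation continues. If the patient is replaced, the event also leaves the denominator.

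Such counts can occur. Protocol 1.3 lists thrombocytopenia among the most common treatment-related reactions and reports an overdosed patient with a nadir of 22 k/µL, all laboratory abnormalities resolving 8 days after the overdose. That was intravenous twice-weekly dosing and no bleed is described, so it shows only that the count range is reachable. Platelet transfusion is permitted (6.8) and could raise the count before the 7-day criterion is met.

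**Working it through.** **Logic check.** The three platelet criteria were applied as written, with a qualifying bleed present throughout. The lower limit of Grade 3 (25,000/mm³) follows from the protocol. Its upper limit is not stated; 50,000/mm³ was assumed and does not affect the result.

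| Platelets (/mm³) | 3 days | 6 days | 7 days |
|---|---|---|---|
| 9,999 | DLT (criterion 3) | DLT (3) | DLT (1, 3) |
| 10,000 | none met | none met | DLT (1) |
| 15,000 | none met | none met | DLT (1) |
| 24,999 | none met | none met | DLT (1) |
| 25,000 | DLT (2) | DLT (2) | DLT (2) |
| 40,000 | DLT (2) | DLT (2) | DLT (2) |

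The uncovered region is 10,000 to below 25,000/mm³ for under 7 days. Reading criterion 2 as Grade 3 or higher makes all six empty cells DLTs and changes no other cell.

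**What happens to an uncovered patient.** There are two routes, and the text does not settle which applies.

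- *Route A.* Section 6.5.1 permits no Cycle 1 modification without a DLT, so all three doses are given and the patient counts as DLT-free.
- *Route B.* The Day 8 or Day 15 dose is withheld under Table 6-2. The dose was missed for a reason other than a DLT, so the patient is replaced and is not DLT-evaluable.

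**Effect on escalation.** The plan gives no operating characteristics for the 3+3 scheme. Its only stated probabilities (83% and 80%, Protocol 8.1.1) concern organ response in the expansion cohorts and do not enter here.

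Under Protocol 6.4, escalation follows 0 of 3, or 1 of 3 and then 0 of 3. With per-patient counted DLT probability q:

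P(escalate) = (1 − q)³ + 3q(1 − q)⁵

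Let p be the full DLT rate with every event counted and u the rate of uncovered events. Both are assumptions. Route A uses q = p − u. Route B uses q = (p − u)/(1 − u), because replaced patients leave the denominator.

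For p = 0.33, all counted: 0.67³ + 3(0.33)(0.67⁵) = 0.301 + 0.134 = 0.434.

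With u = 0.01, route A: q = 0.32, giving 0.68³ + 3(0.32)(0.68⁵) = 0.314 + 0.140 = 0.454.

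With u = 0.01, route B: q = 0.32/0.99 = 0.323, giving 0.448.

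| p | u | All counted | Route A | Route B |
|---|---|---|---|---|
| 0.25 | 0.01 | 0.600 | 0.622 | 0.616 |
| 0.25 | 0.02 | 0.600 | 0.643 | 0.633 |
| 0.25 | 0.05 | 0.600 | 0.709 | 0.686 |
| 0.33 | 0.01 | 0.434 | 0.454 | 0.448 |
| 0.33 | 0.02 | 0.434 | 0.474 | 0.461 |
| 0.33 | 0.05 | 0.434 | 0.536 | 0.505 |

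The rise is about 1 to 2 percentage points at u = 1% and 7 to 11 at u = 5%. The 5% rows are illustrative only.

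**The case against.** The strongest reply is that the gap may be nearly empty. The bleed is itself an adverse event, and the general nonhematologic criterion makes it a DLT if graded 3 or higher. How a bleed of more than 100 cc, or one needing transfusion, is graded depends on CTCAE 4.03, which the protocol cites but does not reproduce. This stands as a limit on size: the documents do not show that any qualifying bleed grades below 3. It does not remove the point, because the protocol defines the bleed by volume or transfusion rather than by grade, and if the general criterion caught every such bleed the separate bleeding criterion would be redundant.

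Second, intent was very probably Grade 3 or higher. Patients enter with platelets of at least 75 × 10⁹/L (5.1), so a fall below 25,000/mm³ passes through the Grade 3 range, and a sensible investigator would call the event a DLT. That is likely, but it means the count rests on readers departing from the text.

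Third, there are backstops. Cycle 2 needs platelets of at least 75 × 10⁹/L (6.5.2.1), so the delay criterion may catch some cases. More conservative escalation is allowed for safety (4.1, 6.4), safety data are reviewed throughout (Protocol 9.1.1, SAP 4), and RP2D selection weighs Grade 3/4 AEs and SAEs (6.4). The event would therefore be seen. But the review provisions are discretionary, and none corrects the DLT count or the replacement rule.

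Fourth, no rate is documented, and the oral weekly study C16004 had no treatment-related AE of Grade 3 or higher at its cutoff (1.3). This stands, and is why the effect is called probably small.

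**Conclusion.** The concern holds. As written, the bleeding criterion counts the milder cytopenia and omits the more severe one at 10,000 to below 25,000/mm³ for under 7 days. An event is lost from the DLT count only if the bleed is graded below 3, is not a Grade 2 or greater toxicity requiring discontinuation, and does not delay Cycle 2 by more than 2 weeks. Within that window the patient is counted as DLT-free or replaced, and both errors favour escalation.

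The logic rests on the protocol text alone. The size rests on assumed event rates. A rise of 1 to 2 percentage points in the probability of escalating, at an assumed 1% uncovered rate, is the more reasonable guide, and the true effect could be smaller.

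The febrile neutropenia wording is a lesser instance of the same slip, since a Grade 3 or higher infection may be caught by the nonhematologic criterion.

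**What to change.** In Protocol 6.3.1, insert *or higher* after *Grade 3* in the thrombocytopenia-with-bleeding criterion and in the febrile neutropenia limb. Then re-check every Cycle 1 Grade 4 cytopenia already ruled not to be a DLT, including patients replaced for missed Cycle 1 doses. If escalation is already complete, the re-check still matters, because it tests whether the MTD rests on a correct count.

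The SAP needs no change; it uses the DLT classification without redefining it. The cost is a few words in one section and a short review of cases. The downside is that an event now missed may count as a DLT and so add 3 patients at a level or stop it.
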